### **5.14 Criteria for Removal from Study Treatment and/or Study Itself**

For patients who are unable to tolerate the protocol-specified dosing schedule, dose adjustments are permitted in order to keep the patient on study drug. If administration of BKM120 must be interrupted because of unacceptable toxicity, drug dosing will be interrupted or modified according to rules described in Table 11. Toxicity will be assessed using the NIH-NCI Common Terminology Criteria for Adverse Events, version 4.0.

[http://evs.nci.nih.gov/ftp1/CTCAE/CTCAE\\_4.03\\_2010-06-14\\_QuickReference\\_8.5x11.pdf](http://evs.nci.nih.gov/ftp1/CTCAE/CTCAE_4.03_2010-06-14_QuickReference_8.5x11.pdf)

The reason for study treatment discontinuation and/or study removal and the date the participant was removed must be documented in the case report form (CRF). Alternative care options will be discussed with the participant.

Reasons that a patient may discontinue study treatment and/or discontinue participation in a clinical study are considered to constitute one of the following:

1. adverse event(s)
2. abnormal laboratory value(s)
3. abnormal test procedure result(s)

4. disease progression
5. protocol violation
6. subject withdrew consent
7. lost to follow-up
8. administrative problems
9. death

A QACT Treatment Ended/Off Study Form should be filled out when a participant completes study treatment and again when the participant comes off study. This form can be found on the QACT website or obtained from the QACT registration staff.

In the event of unusual or life-threatening complications, investigators must immediately notify the Overall PI, [name] at [contact] or page at [contact].

## 6. DOSING DELAYS/DOSE MODIFICATIONS

**Table 11: BKM120 dose level modification guidelines: Criteria for interruption and re-initiation of BKM120 treatment**

Recommended Dose Modifications for BKM120	
Worst toxicity (CTCAE Grade)**	Recommended Dose Modifications
No toxicity	Maintain dose level
HEMATOLOGICAL	
Neutropenia (ANC)	
Grade 1 (ANC < LLN – 1.5 x 10  /L) Grade 2 (ANC < 1.5 – 1.0 x 10  /L)	Maintain dose level
Grade 3 (ANC < 1.0 – 0.5 x 10  /L) Grade 4 (ANC < 0.5 x 10  /L)	Omit dose until resolved to ≤ Grade 1, then: 
 
• If resolved in ≤ 7 days, then maintain dose level
 
• If resolved in > 7 days, then ↓ 1 dose level
 

Febrile neutropenia (ANC < 1.0 x 10  /L, fever ≥ 38.5°C)	Omit dose until resolved, then ↓ 1 dose level
Thrombocytopenia	
Grade 1 (PLT < LLN – 75 x 10  /L) Grade 2 (PLT < 75 – 50 x 10  /L)	Maintain dose level
Grade 3 (PLT < 50-25 x 10  /L)	Omit dose until resolved to ≤ Grade 1, then: 
 
• If resolved in ≤ 7 days, then maintain dose level
 
• If resolved in > 7 days, then ↓ 1 dose level
 

Grade 4 (PLT < 25 x 10  /L)	Omit dose until resolved to ≤ Grade 1, then ↓ 1 dose level

Recommended Dose Modifications for BKM120	
Worst toxicity (CTCAE Grade)**	Recommended Dose Modifications
HEPATIC	
Bilirubin (*for patients with Gilbert Syndrome these dose modifications apply to changes in direct bilirubin only)	Will be fractionated if elevated
Grade 1 (> ULN – 1.5 x ULN)	Maintain dose level with LFTs* monitored as per protocol
Grade 2 (> 1.5 – 3.0 x ULN) with ALT or AST ≤ 3.0 x ULN	Omit dose until resolved to ≤ Grade 1, then: 
 
• If resolved in ≤ 7 days, then maintain dose level
 
• If resolved in > 7 days, then ↓ 1 dose level
 

Grade 3 (> 3.0 – 10.0 x ULN) with ALT or AST ≤ 3.0 x ULN	Omit dose until resolved to ≤ Grade 1, then: 
 
• If resolved in ≤ 7 days, ↓ 1 dose level
 
• If resolved in > 7 days discontinue patient from study treatment
 

Grade 4 (> 10.0 x ULN)	Omit dose and discontinue patient from study treatment
AST or ALT	
Grade 1 (> ULN – 3.0 x ULN)	Maintain dose level with LFTs* monitored as per protocol
Grade 2 (> 3.0 – 5.0 x ULN) without bilirubin elevation to > 2.0 x ULN	Omit dose until resolved to ≤ grade 1, then 
 
• If resolved in ≤ 7 days, then maintain dose level
 
• If resolved in > 7 days, then ↓ 1 dose level
 

Grade 3 (> 5.0 - 20.0 x ULN) without bilirubin elevation to > 2.0 x ULN	Omit dose until resolved to ≤ Grade 1 then: 
 
• If resolved in ≤ 7 days, then maintain dose level
 
• If resolved in > 7 days, then ↓ 1 dose level
 

Grade 4 (> 20.0 x ULN) without bilirubin elevation to > 2.0 x ULN	Omit dose until resolved to ≤ Grade 1 , then ↓ 1 dose level
AST or ALT and concurrent Bilirubin	
AST or ALT > 3.0 x ULN and total bilirubin > 2.0 x ULN	Discontinue study treatment permanently.
* LFTs include albumin, ALT, AST, total bilirubin (fractionated if total bilirubin > 2.0 x ULN), alkaline phosphatase (fractionated if alkaline phosphatase is grade 2 or higher) and GGT.	
Monitoring (*for patients with Gilbert Syndrome: total and direct bilirubin must be monitored, intensified monitoring applies to changes in direct bilirubin only; the monitoring includes the following LFTs: albumin, ALT, AST, total bilirubin (fractionated if total bilirubin > 2.0 x ULN), alkaline phosphatase (fractionated if alkaline phosphatase is grade 2 or higher) and GGT.	
ENDOCRINE/METABOLIC	
Fasting Plasma Glucose (FPG)	
Grade 1 (> ULN - 160 mg/dL) [> ULN - 8.9 mmol/L]	Maintain dose level, check FPG every week 
 
• initiate or intensify medication with appropriate anti-diabetic treatment as per investigator's discretion
 
• instruct patient to follow dietary guidelines according to local and/or institutional standards for management of diabetes mellitus (such as those provided by the American Diabetes Association) during the study
 
• Consider use of oral anti-hyperglycemic therapy such as metformin (or intensify existing medications)
 
• check FPG at least weekly for 8 weeks, then continue checking at least every 2 weeks
 

Recommended Dose Modifications for BKM120	
Worst toxicity (CTCAE Grade)**	Recommended Dose Modifications

Grade 2 (>160 – 250 mg/dL) [> 8.9 - 13.9 mmol/L]
	
 
• If signs or symptoms of hyperglycemia (for example, mental status changes, excessive thirst, polyuria) manage as for Grade 3 hyperglycemia (see below).
 
• If asymptomatic, maintain dose and re-check FPG within 24 hours. If grade worsens or improves then follow specific grade recommendations. If FPG remains at Grade 2:               
 
• maintain dose level and monitor FPG at least weekly until FPG resolves to ≤ Grade 1
 
• initiate or intensify medication with appropriate anti-diabetic treatment such as metformin; consider adding a second oral agent if no improvement after several days
 
• instruct patient to follow dietary guidelines according to local and/or institutional standards for management of diabetes mellitus (such as those provided by the American Diabetes Association) during the study
 
• If FPG does not resolve to ≤ Grade 1 within 14 days after institution of appropriate anti-diabetic treatment reduce BKM120 by 1 dose level
 
 
 
 
Continue with anti-diabetic treatment and check FPG at least weekly for 8 weeks, then continue checking at least every 2 weeks


Grade 3 (> 250 - 500 mg/dL) [> 13.9 - 27.8 mmol/L]
	
 
• Omit BKM120, initiate or intensify medication with appropriate anti-diabetic treatment, re-check FPG within 24 hours. If grade worsens or improves then follow specific grade recommendations. If FPG remains at Grade 3:               
 
• administer intravenous hydration and intervention for electrolyte/ketoacidosis/hyperosmolar disturbances as clinically appropriate
 
• continue to omit BKM120
 
• monitor FPG at least twice weekly until FPG resolves to ≤ Grade 1
 
• If FPG resolves to ≤ Grade 1 in 7 days or less, then re-start BKM120 and ↓ 1 dose level
 
• If FPG remains greater than Grade 1 severity for more than 7 days, then discontinue patient from BKM120
 
• initiate or continue anti-diabetic treatment as appropriate                   
 
• instruct patient to follow dietary guidelines according to local and/or institutional standards for management of diabetes mellitus (such as those provided by the American Diabetes Association) during the study
 
• consider use of oral anti-hyperglycemic therapy such as metformin
 
 
 
• check FPG at least weekly for 8 weeks, then continue checking at least every 2 weeks
 
 
 
 
For non-fasting plasma glucose >250-500 mg/dL (> 13.9 - 27.8 mmol/L) accompanied by signs/symptoms of hyperglycemia (for example, mental status changes, excessive thirst, polyuria), or presence of blood or urine ketones, omit BKM120 and following guidance for management of Grade 3 fasting plasma glucose (FPG)

Recommended Dose Modifications for BKM120	
Worst toxicity (CTCAE Grade)**	Recommended Dose Modifications
Grade 4 (> 500 mg/dL) [<math>\geq</math> 27.8 mmol/L]	
 
• immediately omit BKM120, initiate or intensify medication with appropriate anti-diabetic treatment, re-check within 24 hours. if grade improves then follow specific grade recommendations. If FPG is confirmed at Grade 4:               
 
• administer intravenous hydration and intervention for electrolyte/ketoacidosis/hyperosmolar disturbances as clinically appropriate
 
• discontinue patient from BKM120
 
• instruct patient to follow dietary guidelines according to local and/or institutional standards for management of diabetes mellitus (such as those provided by the American Diabetes Association) during the study
 
• consider use of oral anti-hyperglycemic therapy such as metformin
 
• check FPG at least weekly for 8 weeks, then continue checking at least every 2 weeks if clinically indicated
 
 
 
 
For non-fasting plasma glucose >500 mg/dL (> 27.8 mmol/L) accompanied by signs/symptoms of hyperglycemia (for example, mental status changes, excessive thirst, polyuria), or presence of blood or urine ketones, discontinue BKM120 and following guidance for management of Grade 4 fasting plasma glucose (FPG).

Recommended Dose Modifications for BKM120	
Worst toxicity (CTCAE Grade)**	Recommended Dose Modifications
CARDIAC	
Cardiac – Left Ventricular systolic dysfunction	
Asymptomatic, resting ejection fraction 50 – 40%; or 10-20% drop from baseline	Maintain dose level
Symptomatic, responsive to intervention, ejection fraction 39 – 20% or > 20% drop from baseline	Omit dose until resolved to ≤ Grade 1, then ↓ 1 dose level LVEF measurement to be repeated, if not resolved to ≤ Grade 1 within 3 weeks, permanently discontinue patient from BKM120
Refractory or poorly controlled, ejection fraction < 20%	Omit dose and discontinue patient from BKM120
Cardiac – QTc prolongation	
QTcF > 500 ms (≥ Grade 3) or > 60 ms change from baseline on at least two separate ECGs	First Occurrence: 
 
• omit BKM120
 
• Perform an analysis of serum potassium and magnesium, and if below lower limit of normal, correct with supplements to within normal limits. Concomitant medication usage must be reviewed.
 
• Perform a repeat ECG within one hour of the first QTcF of > 500 ms
 
• If QTcF remains > 500 ms, repeat ECG as clinically indicated, but at least once a day until the QTcF returns to < 480 ms.
 
• Once QTcF prolongation has resolved, BKM120 may be restarted at a one lower dose level
 
 Second Occurrence: 
 
• discontinue patient from BKM120
 

Other Cardiac Events	
Grade 1 or 2	Maintain dose level
Grade 3	Omit dose until resolved to ≤ Grade 1, then ↓ 1 dose level
Grade 4	Omit dose and discontinue patient from BKM120
OTHER	
Mood alteration	
* See Table 4 for toxicity grading of mood questionnaires. Questionnaire scores should be considered when assigning the AE Grade but psychiatric consult, if required, may determine the grade	
Grade 1 (or Grade 2 anxiety if present at baseline)	Maintain dose level  Note: If question 9 on the PHQ-9 has a positive response, or worsens in severity, the patient should be referred for psychiatric consult regardless of the total questionnaire score

Recommended Dose Modifications for BKM120	
Worst toxicity (CTCAE Grade)**	Recommended Dose Modifications
Grade 2 (for Anxiety only, if worsened from baseline)	
Institute appropriate co-medication under the guidance of the psychiatrist. Maintain dose level.
 
 
If the condition does not resolve to <math>\leq</math> Grade 1 within 14 days despite medical treatment; then <math>\downarrow</math> 1 dose level (continue to co-medicate)
 
 
Note: If question 9 on the PHQ-9 has a positive response, or worsens in severity, the patient should be referred for psychiatric consult regardless of the total questionnaire score

Grade 3	
Omit dose until resolved to <math>\leq</math> Grade 1, then <math>\downarrow</math> 1 dose level (co-medicate)
 
Note: If question 9 on the PHQ-9 has a positive response, or worsens in severity, the patient should be referred for psychiatric consult regardless of the total questionnaire score

Grade 4	
Omit dose and discontinue patient from study
 
Note: If question 9 on the PHQ-9 has a positive response, or worsens in severity, the patient should be referred for psychiatric consult regardless of the total questionnaire score

Rash	
Grade 1	Maintain dose level. Consider to initiate appropriate skin toxicity therapy (such as antihistamines, topical corticosteroids)
Grade 2	Maintain dose level. Initiate/intensify appropriate skin toxicity therapy (such as antihistamines, topical corticosteroids)
Grade 3	
Omit dose until resolved to CTCAE Grade <math>\leq</math> 1, then:
 
 
If resolved in <math>\leq</math> 7 days, <math>\downarrow</math> 1 dose level
 
If resolved in <math>></math> 7 days (despite appropriate skin toxicity therapy), discontinue patient from BKM120
 

Grade 4	Omit dose and discontinue patient from BKM120
Fatigue (asthenia)	
Grade 1 or 2	Maintain dose level
Grade 3	
Omit dose until resolved to <math>\leq</math> Grade 1, then:
 
 
If resolved in <math>\leq</math> 7 days, maintain dose level
 
If resolved in <math>></math> 7 days, <math>\downarrow</math> 1 dose level
 

Grade 4	Omit dose and discontinue patient from BKM120
Other non-hematological adverse events	
Grade 1 or 2	Maintain dose level
Grade 3	Omit dose until resolved to $\leq$ Grade 1, then $\downarrow$ 1 dose level
Grade 4	
Omit dose and discontinue patient from study
 
Note: Omit dose for <math>\geq</math> Grade 3 vomiting or Grade 3 nausea only if the vomiting or nausea cannot be controlled with optimal antiemetic

Pneumonitis	See Table 15
** Common Terminology Criteria for Adverse Events (CTCAE) version 4.0.	

Fasting Plasma Glucose (FPG)	
Grade 1 (> ULN - 160 mg/dL) [ > ULN - 8.9 mmol/L]	
Maintain dose level, check FPG every week
 
 
initiate or intensify medication with appropriate anti-diabetic treatment as per investigator's discretion
 
instruct patient to follow dietary guidelines according to local and/or institutional standards for management of diabetes mellitus (such as those provided by the American Diabetes Association) during the study
 
Consider use of oral anti-hyperglycemic therapy such as metformin (or intensify existing medications)
 
Check FPG at least weekly for 8 weeks, then continue checking at least every 2 weeks
 

Grade 2 (>160 - 250 mg/dL) [ 8.9 - 13.9 mmol/L]	
 
If signs or symptoms of hyperglycemia (for example, mental status changes, excessive thirst, polyuria) manage as for Grade 3 hyperglycemia (see below).
 
If asymptomatic, maintain dose and re-check FPG within 24 hours. If grade worsens or improves then follow specific grade recommendations. If FPG remains at Grade 2: 
 
maintain dose level and monitor FPG at least weekly until FPG resolves to ≤ Grade 1
 
initiate or intensify medication with appropriate anti-diabetic treatment such as metformin; consider adding a second oral agent if no improvement after several days
 
instruct patient to follow dietary guidelines according to local and/or institutional standards for management of diabetes mellitus (such as those provided by the American Diabetes Association) during the study
 
If FPG does not resolve to ≤ Grade 1 within 14 days after institution of appropriate anti-diabetic treatment reduce BKM120 by 1 dose level
 
 
 
Continue with anti-diabetic treatment and check FPG at least weekly for 8 weeks, then continue checking at least every 2 weeks
 

Grade 3 (> 250 - 500 mg/dL) [ 13.9 - 27.8 mmol/L]	
 
Omit BKM120, initiate or intensify medication with appropriate anti-diabetic treatment, re-check FPG within 24 hours. If grade worsens or improves then follow specific grade recommendations. If FPG remains at Grade 3: 
 
administer intravenous hydration and intervention for electrolyte/ketoacidosis/hyperosmolar disturbances as clinically appropriate
 
continue to omit BKM120
 
monitor FPG at least twice weekly until FPG resolves to ≤ Grade 1
 
If FPG resolves to ≤ Grade 1 in 7 days or less, then re-start BKM120 and ↓ 1 dose level
 
If FPG remains greater than Grade 1 severity for more than 7 days, then discontinue patient from BKM120
 
initiate or continue anti-diabetic treatment as appropriate 
 
instruct patient to follow dietary guidelines according to local and/or institutional standards for management of diabetes mellitus (such as those provided by the American Diabetes Association) during the study
 
consider use of oral anti-hyperglycemic therapy such as metformin
 
 
 
check FPG at least weekly for 8 weeks, then continue checking at least every 2 weeks
 
 
 
 
For non-fasting plasma glucose >250-500 mg/dL (> 13.9 - 27.8 mmol/L) accompanied by signs/symptoms of hyperglycemia (for example, mental status changes, excessive thirst, polyuria), or presence of blood or urine ketones, omit BKM120 and following guidance for management of Grade 3 fasting plasma glucose (FPG)

Grade 4 (> 500 mg/dL) [≥ 27.8 mmol/L]	
 
immediately omit BKM120, initiate or intensify medication with appropriate anti-diabetic treatment, re-check within 24 hours. if grade improves then follow specific grade recommendations. If FPG is confirmed at Grade 4: 
 
administer intravenous hydration and intervention for electrolyte/ketoacidosis/hyperosmolar disturbances as clinically appropriate
 
discontinue patient from BKM120
 
instruct patient to follow dietary guidelines according to local and/or institutional standards for management of diabetes mellitus (such as those provided by the American Diabetes Association) during the study
 
 
 

	
 
• consider use of oral anti-hyperglycemic therapy such as metformin
 
• check FPG at least weekly for 8 weeks, then continue checking at least every 2 weeks if clinically indicated
 
 
For non-fasting plasma glucose >500 mg/dL (> 27.8 mmol/L) accompanied by signs/symptoms of hyperglycemia (for example, mental status changes, excessive thirst, polyuria), or presence of blood or urine ketones, discontinue BKM120 and following guidance for management of Grade 4 fasting plasma glucose (FPG).

--	--

If the toxicity is due to BKM120, only BKM120 will be dose reduced by one level according to the following schedule below. If toxicity occurs at BKM120 20 mg level, BKM120 will be held.

Dose Level	Dose of BKM120 (mg, daily)
Level E	100
Level D	80
Level C	60
Level B	40
Level A	20

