## **1. OBJECTIVES**

### **1.1 Study Design**

This phase Ib study is combining standard chemoradiotherapy with weekly cisplatin and BKM120 to assess tolerability of this combination in high risk patients with locally advanced Squamous Cell Carcinoma of the Head and Neck (SCCHN). We will also obtain preliminary information about the efficacy of this treatment.

The design of this study follows a classical 3+3 design with a planned expansion cohort of 10 patients when after determination of MTD.

BKM120 will start **2 weeks** prior to first dose of cisplatin and radiation start. Radiotherapy will be standard of care.

Patients will be assessed weekly for adverse events for the duration of the treatment (2 weeks of BKM120 and 7 weeks of CRT = 9 weeks) and every 2 weeks after conclusion of CRT during the first month, then monthly for 3 months, then every 3 months, until first progression, death, or 2 years from study entry whichever occurs first.

Fresh biopsies will be obtained prior to BKM120 and after 7-10d of treatment but prior to start of radiation treatment. Biopsies will be snap frozen and used for correlative studies. Biopsies are optional but encouraged in patients with accessible tumors.

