**Table 9: Criteria for Defining Dose-Limiting Toxicities**

TOXICITY	ANY OF THE FOLLOWING CRITERIA
Hematologic a	≥ CTCAE grade 3 neutropenia for > 7 consecutive days
	CTCAE grade 3 thrombocytopenia for > 7 consecutive days
	CTCAE grade 4 thrombocytopenia
	Febrile neutropenia (ANC < 1.0 x 10  /L, fever ≥ 38.5°C)
Renal	Serum creatinine ≥ 2.0 x ULN to ≤ 3.0 x ULN for > 7 consecutive days
	> CTCAE grade 3 serum creatinine
Hepatic b	Total bilirubin ≥ 2xULN to ≤ 3.0 x ULN for > 7 consecutive days
	> CTCAE grade 3 total bilirubin
	CTCAE grade 3 AST or ALT for > 7 consecutive days
	CTCAE grade 4 AST or ALT
Endocrine	Grade 2 hyperglycemia (confirmed with a repeat FPG within 24 hours) that does not resolve to grade 0 within 14 consecutive days (after initiation of glimepiride, metformin or glibenclamide)
	≥ Grade 3 hyperglycemia (confirmed with a repeat FPG within 24 hours)
Metabolic/Laboratory	CTCAE grade 3 asymptomatic amylase and/or lipase, not reversible to ≤ CTCAE grade 2 for > 7 consecutive days
	CTCAE grade 4 asymptomatic amylase and/or lipase
Pancreatitis	≥ CTCAE grade 2
Cardiac	Cardiac toxicity ≥ CTCAE grade 3 or cardiac event that is symptomatic or requires medical intervention
	Clinical signs of cardiac disease, such as unstable angina or myocardial infarction, or Troponin ≥ CTCAE grade 3
Neurotoxicity	≥ 1 CTCAE grade level increase
Mood alteration	CTCAE grade 2 mood alteration that does not resolve to ≤ grade 1 within 14 days despite medical treatment (for Anxiety only, if worsened from baseline)
	≥ CTCAE grade 3 mood alteration
Dermatologic	Any phototoxicity ≥ CTCAE grade 2, or skin toxicity (rash) resulting in interruption of BKM120 for > 21 consecutive days
Other adverse events	≥ CTCAE grade 3 adverse events (excluding ≥ CTCAE grade 3 elevations in

	alkaline phosphatase)
	≥ CTCAE grade 3 vomiting or CTCAE grade 3 nausea despite the use of standard anti-emetics
	≥ CTCAE grade 3 diarrhea despite the use of optimal anti-diarrhea treatments
	CTCAE grade 3 fatigue (asthenia) for > 7 consecutive days CTCAE grade 4 fatigue (asthenia)

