
a ≥ CTCAE grade 3 anemia will not be considered DLT unless judged to be a hemolytic process secondary to study drug. ≥ CTCAE grade 3 lymphopenia will not be considered DLT unless clinically significant.
 
b For any grade 3 or 4 hepatic toxicity that does not resolve within 7 days to ≤ grade 1 (or ≤ grade 2 if liver infiltration with tumor present), an abdominal CT scan has to be performed to assess if it is related to disease progression.
 
A single patient is assumed not to tolerate the dose if he/she experiences at least one DLT. If a lower grade AE leads to a dose interruption of more than 7 doses of BKM120, this AE will be considered as DLT.
 
If the 2nd occurrence of an initially non-dose limiting toxicity (e.g., grade 3 AST that resolved to ≤ grade 1 within 7 days at 1st occurrence) leads to a dose reduction ( Section 6) within 28 days of the first dose of BKM120, this will be considered a DLT.
	

The investigator must notify the sponsor immediately of any unexpected ≥ CTCAE grade 3 adverse events or laboratory abnormalities. Prior to enrolling patients into a higher dose level, ≥ CTCAE grade 2 adverse events will be reviewed for all patients at the current dose level.

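### Table 11's bilirubin rows overlap its permanent-stop row when only one transaminase exceeds 3.0 x ULN, and no precedence is given

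*Combined protocol and SAP*

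**What the plan says.** The hepatic part of Table 11 in Section 6 has three blocks that bear on a patient with raised bilirubin and raised transaminases.

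- **Bilirubin.** The grade 2 row covers "Grade 2 (> 1.5 – 3.0 x ULN) with ALT or AST ≤ 3.0 x ULN". BKM120 is held until recovery to grade 1 or better. It then resumes at the same dose if that took 7 days or fewer, and one level lower if it took longer. The grade 3 row covers "Grade 3 (> 3.0 – 10.0 x ULN) with ALT or AST ≤ 3.0 x ULN". BKM120 resumes one level lower if recovery took 7 days or fewer; otherwise treatment ends. Grade 4, above 10.0 x ULN, ends treatment.
- **AST or ALT.** The grade 2 row reads "Grade 2 (> 3.0 – 5.0 x ULN) without bilirubin elevation to > 2.0 x ULN", and the grade 3 and 4 rows carry the same bilirubin exclusion. All three allow a restart.
- **AST or ALT with concurrent bilirubin.** For "AST or ALT > 3.0 x ULN and total bilirubin > 2.0 x ULN" the action is to stop study treatment for good.

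Section 5.14 makes the table operative: "drug dosing will be interrupted or modified according to rules described in Table 11".

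Two entries in Table 9 (Section 5.5) link this to DLT counting. One hepatic criterion is "Total bilirubin ≥ 2xULN to ≤ 3.0 x ULN for > 7 consecutive days". A note below the table adds: "If a lower grade AE leads to a dose interruption of more than 7 doses of BKM120, this AE will be considered as DLT".

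**The concern.** A stopping rule for liver injury should give one answer per patient. Here, a combined transaminase and bilirubin abnormality that one row says must end treatment can be managed under another row that permits rechallenge, in the grade 2 case at the same dose.

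The choice of row can also change the primary endpoint data. Table 9 has no criterion for combined liver injury, so a short-lived grade 2 event may count as a DLT only through the number of doses lost, and that number depends on which Table 11 row was followed. In a 3+3 design one patient matters: under Table 7 it turns 0 of 3 into 1 of 3, or 1 of 6 into 2 of 6.

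**Working it through.** The plan gives no figure to reproduce. The check is on the logic of the rows, followed by a dose count. All laboratory values are multiples of ULN, and the logic applies to patients without Gilbert syndrome.

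**1. Conditions as written**

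- Bilirubin grade 2 or 3 row (hold, possible restart): 1.5 < bilirubin ≤ 10.0 and (ALT ≤ 3.0 or AST ≤ 3.0).
- Concurrent row (permanent stop): bilirubin > 2.0 and (ALT > 3.0 or AST > 3.0).

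Both hold when 2.0 < bilirubin ≤ 10.0, at least one transaminase is ≤ 3.0 and at least one is > 3.0. With two transaminases, that means exactly one is > 3.0.

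**2. Grid check.** The rows were evaluated at 12 bilirubin values (0.9 to 10.1) and 7 values each of ALT and AST (0.9 to 21).

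| Wording of the bilirubin rows | Points meeting both rows | Abnormal points with no row |
|---|---|---|
| ALT *or* AST ≤ 3.0 | 144 | 0 |
| ALT *and* AST both ≤ 3.0 | 0 | 0 |

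The 144 is as expected: 6 bilirubin values lie above 2.0 and up to 10.0; 3 transaminase values are ≤ 3.0 and 4 are > 3.0, so 2 x 3 x 4 = 24 pairs have exactly one above; 6 x 24 = 144. This counts grid points and says nothing about frequency.

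**3. Examples under the present wording**

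- Bilirubin 2.5, ALT 4, AST 2.5: grade 2 bilirubin row and concurrent row.
- Bilirubin 5, ALT 2, AST 4: grade 3 bilirubin row and concurrent row.
- Bilirubin 2.5, ALT 4, AST 4: concurrent row only.

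**4. Doses at stake.** Section 1.1 gives the treatment period as "2 weeks of BKM120 and 7 weeks of CRT = 9 weeks", so daily dosing covers 9 x 7 = 63 days. For an event found on day d, before that day's dose:

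- doses lost with a permanent stop = 63 − d + 1 = 64 − d;
- further doses if 7 are omitted and dosing resumes = 64 − d − 7 = 57 − d, with a minimum of 0.

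| Day found | Lost with permanent stop | Further doses under bilirubin row |
|---|---|---|
| 8 | 56 | 49 |
| 15 (CRT day 1) | 49 | 42 |
| 50 | 14 | 7 |
| 57 | 7 | 0 |

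The count assumes no radiotherapy break. If radiotherapy, given 5 days a week, ends on a Friday, BKM120 also ends about 2 days earlier. The day 15 figures then become about 47 and 40.

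**5. DLT status of the first example (found on day 15, resolving within 7 days)**

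- Bilirubin row: ALT 4 is grade 2 and bilirubin 2.5 lasts no more than 7 days, so no hepatic criterion in Table 9 is met. At most 7 doses are lost, which is not more than 7. Result: 0 DLT.
- Concurrent row: 49 doses are lost. Result: 1 DLT, if a permanent stop counts as a dose interruption under the note to Table 9. On that reading the two rows give different DLT results for any such event found up to day 56, when 64 − 56 = 8 doses are lost.

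**The case against.** The best reply is that the table, read as a whole, points to one answer. In the example, the ALT grade 2 row excludes the patient because bilirubin exceeds 2.0 x ULN, so only the concurrent row deals with the ALT. That row has its own heading and an unqualified action, and is the more specific of the two. A careful clinician would probably follow it. This stands as evidence of intent, but it does not supply the missing rule. The column heading selects by worst CTCAE grade, and the concurrent row has no grade, so the heading cannot rank it. Section 5.7, Section 5.14, Section 6 and the liver toxicity guidance in Section 7.1 give no precedence either. The concurrent row also uses the same connective to mean either enzyme, which supports the literal reading of the bilirubin rows.

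The DLT contrast is open to a fair challenge. Sections 5.4, 5.6 and 5.7 name interruption and discontinuation separately, so treating a permanent stop as an interruption of more than 7 doses is the natural reading but still an inference. The contrast also needs recovery within 7 days: bilirubin still at 2 to 3 x ULN after 7 days is a DLT under either row.

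Exposure is narrow. Entry requires normal ALT and AST and, with limited exceptions, normal bilirubin. Section 2.2.8.3 reports liver events as frequent at 100 mg/day (22 of 55 patients, 40.0%, in the first-in-human study), but says that few patients with abnormal liver tests had other signs of impaired function, such as raised bilirubin, at the same time. Review of grade 2 or higher events before escalation, the principal investigator's discretion and the DSMC further limit any effect on escalation.

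**Conclusion.** The concern holds, as a minor point. The overlap is exactly one transaminase above 3.0 x ULN with bilirubin above 2.0 and up to 10.0 x ULN. Both rows stop BKM120 at once and differ only on later rechallenge. They agree when bilirubin is above 10.0 x ULN, and when a grade 3 bilirubin has not recovered within 7 days.

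For the worked patient found on day 15, the difference is 0 against 42 further doses, assuming 7 omitted doses; faster recovery would allow more. Across detection days from 8 onward, the bilirubin row allows from 49 further doses down to none. The difference of 1 against 0 DLT is conditional on the natural reading of the Table 9 note and on recovery within 7 days.

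The documents give no rate for this event, so no expected number of affected patients can be stated. For patients with Gilbert syndrome the limits of the overlap differ, because the bilirubin rows then use direct bilirubin while the concurrent row names total bilirubin. No sample size or other statistical figure in the plan is affected.

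**What to change.** In the grade 2 and grade 3 bilirubin rows of Table 11, replace the transaminase condition with *ALT and AST both ≤ 3.0 x ULN*. The concurrent row then alone governs any transaminase above 3.0 x ULN with total bilirubin above 2.0 x ULN. Bilirubin above 1.5 and up to 2.0 x ULN with a transaminase above 3.0 x ULN falls to the AST/ALT rows, which also hold the drug, so no patient is left without an instruction.

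The cost is a few words in two table rows. Sample size, visits, data collection, Table 9 and the Gilbert provisions stay as they are.
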